5.2 Exclusion Criteria

- Treatment with anti-IL-6, anti-IL-6R antagonists or Janus kinase inhibitor (JAKi) within 48 hours of first dose of study treatment.
- No other investigational therapies as part of another clinical trial with the intent to treat the patient's COVID-19 can be administered while the patient is enrolled in the study.
 - Exception is remdesivir, hydroxychloroquine, convalescent plasma or other treatments being used as compassionate use or under Emergency Use Authorization (EUA) for COVID-19 per Investigator discretion.
- Expected non-COVID-related survival of < 2 months.
- Receipt of non-oncology vaccines containing live virus for prevention of infectious diseases within 4 weeks prior to first dose of study treatment
- History of severe hypersensitivity reaction to any mAb
- Multi-organ failure requiring vasopressors or continuous veno-venous hemofiltration (CVVH) or extracorporeal membrane oxygenation.
- No active systemic bacterial or fungal infection
 - Excludes patients with positive blood cultures not infections like empiric pneumonia, antibiotic coverage, UTIs, etc.
 - Patients with a history of positive bacterial or fungal cultures but on enrollment do not have suspected or known active systemic bacterial or fungal infections are permitted.

5.3 Inclusion of Women and Minorities

All genders, races and ethnic groups are eligible for this trial.

5.4 Subject Recruitment

Subjects will be recruited from the inpatient units at NYP/Columbia University Irving Medical Center. Patients will not receive payment or reimbursement for participation. Every effort will be made to include patients of racial and ethnic minorities who fulfill the eligibility criteria.

A member of the patient's treatment team, the protocol investigator, or research team at NYP/Columbia University Irving Medical Center will identify potential research

participants. If the investigator is a part of the treatment team, s/he will screen the patient as to eligibility, and will discuss the study and the possibility of enrollment in the research study with the patient. The preliminary screen of eligibility will be inpatient hospitalization and confirmed SARS-CoV-2 infection.

Potential subjects that meet these basic criteria will be referred by their treating physician to the investigator, co-investigators, or research staff of the study. Minority patients are well represented at NYP/Columbia University Irving Medical Center, and we expect that they will be well represented in the trial accrual. The principal investigator, [name] will be available to all patients for further questions and information through the contact number that will be provided on the consent form.

During the initial conversation between the investigator/research staff and the patient, the patient may be asked to provide certain health information that is necessary to the recruitment and enrollment process. The investigator/research staff may also review portions of their medical records in order to further assess eligibility. They will use the information provided by the patient and/or medical record to confirm that the patient is eligible and to contact the patient regarding study enrollment. If the patient turns out to be ineligible for the research study, the research staff will destroy all information collected on the patients during the initial conversation and medical records review, except for any information that must be maintained for screening log purposes

5.5 Early Withdrawal of Subjects

5.5.1 *When and How to Withdraw Subjects*

- If at any time the patient develops unacceptable toxicity (e.g. a severe infusion reaction), as determined in consultation with the PI, he/she will be removed from the study treatment but should continue to be followed on the study for clinical outcomes including safety, intubation and mortality.
- If the patient withdraws consent for continued participation, he will be removed from study.

5.5.2 *Data Collection and Follow-up for Withdrawn Subjects*

If subjects withdraw prematurely from the study, follow-up will continue for all subjects. Subjects withdrawn because of unacceptable adverse events will be followed until resolution or stabilization of the adverse event. An attempt will be made to obtain survival information for all subjects for a period of at least 1 year following the time of registration or until death, whichever comes first. This will include attempts to contact subjects via telephone and by certified letter using information available to the investigators and the study team. When possible, at least two attempts will also be made to contact the subject's next of kin to obtain such information while observing relevant privacy laws, when applicable.

6. REGISTRATION PROCEDURES

6.1 CUMC Research Participant Registration

Confirm eligibility as defined in the section entitled Criteria for Subject Eligibility.

Obtain informed consent, by following procedures defined in section entitled Informed Consent Procedures, along with applicable institutional policies and federal regulations.

Only Investigators/Research personnel properly trained and delegated to consent subjects for this protocol will participate in the consenting process. Furthermore, properly delegated/trained Physician Investigators (e.g., MD, MD PhD) are required to sign/verify a protocol specific Eligibility Checklist for each subject enrolled on the study, in addition to providing the relevant source documentation confirmation subject eligibility.

All participants must be centrally registered through the Central Registration Office within Herbert Irving Comprehensive Cancer Center at CUMC prior to initiation of study treatment.

Registration hours are available Monday through Friday from 9:00am – 5:00pm EST (excluding holidays and weekends). Same day patient registrations (and after hour registrations) will be accommodated on a case by case basis provided that the study team has expressed all time sensitive registration concerns/cases in a timely manner to the Central Registration Office.

CPDM Central Registration Procedures:

Within 48 hours of obtaining consent (excluding holidays and weekends), a completed/signed IRB approved informed consent HIPAA form, and demographics forms must be submitted to the CPDM Central Registration Office via an email to [contact] or fax to [contact], with the subject line “AAAS9881 Pending Subject Registration Request (PHI)”. Upon receipt, applicable subject information as well as a “pending eligibility” status will be entered into HICCC’s institutional database. This status will remain until further source documentation is made available to confirm overall patient eligibility. Required materials for all pending registration submissions are as follows:

- Completed/signed IRB approved/stamped Informed Consent Forms, including additional study ICFs (e.g., tissue, DNA, etc.), as applicable.
- The completed/signed IRB approved HIPAA Authorization form
- Completed/signed CPDM ICF checklist
- Completed/signed HICCC personal census form
- Completed/signed CPDM Demographics Note to File

In order to confirm eligibility status, Investigators/designees (e.g., study specific Clinical Research Coordinator/Research Nurse, etc.) must submit the following documentation to the Central Registration Office via email or fax:

- The completed/signed study specific Eligibility Checklist (signed by a Physician level Investigator)
- Copies of source documentation necessary for each item to be verified on the CPDM specific Eligibility Checklist, including but not limited to:
 - Copy of required laboratory test and procedure reports (e.g., hematology, serum chemistry, pregnancy test when applicable, MRI reports, CT/bone scans, etc.)
 - Copy of pathology and surgical reports
 - Copy of clinic note(s) or other appropriate medical records capturing the consent process information, along with providing source documentation of any other items needed for screening/eligibility that are not captured in other source document forms (e.g., positive investigator statements of unique eligibility items not captured via other direct source documentation, concomitant medication lists, etc.)
 - Protocol deviation/waiver approvals (if applicable)
- **Please note:** subject line of email or fax should include the following: “AAAS9881 Complete Subject Registration Request (PHI)”.

Upon receipt of the above mentioned documentation, participant eligibility information will be verified by a qualified Central Registration Registrar. If any questions arise during the review process, queries in the form of emails will be addressed to the applicable study team personnel for clarification prior to enrollment. All applicable finalized registration/eligibility information will then be entered into HICCC’s institutional CTMS database by the Central Registration Registrar. Upon completion, an official subject registration notification email will be sent to the PI/research team which will include eligibility/enrollment status, as well as subject ID information. Protocol therapy may not be initiated prior to receipt of this notification from the Central Registration Office.

All screen fail/ineligible subjects, as well as subject’s who withdraw consent prior to enrollment/initiation of protocol therapy must be submitted to the Central Registration office in a manner analogous to the procedures noted above. Applicable source documentation will be required within the corresponding submissions.

6.2 Informed Consent Procedures

Before protocol-specified procedures are carried out, consenting professionals will explain full details of the protocol and study procedures as well as the risks involved to participants prior to their inclusion in the study. Participants will also be informed that they are free to withdraw from the study at any time. All participants must review the IRB/PB-approved consent form and indicate their consent to participate. This consent form meets the requirements of the Code of Federal

Regulations and the Institutional Review Board/Privacy Board of this Center. The consent form will include the following:

1. The nature, objectives, potential risks and benefits of the intended study.
2. The length of study and the likely follow-up required.
3. Alternatives to the proposed study. This will include available standard and investigational therapies. In addition, patients will be offered an option of supportive care for therapeutic studies.
4. The name of the investigator(s) responsible for the protocol.
5. The right of the participant to accept or refuse study interventions/interactions and to withdraw from participation at any time.

Before any protocol-specific procedures can be carried out, the consenting professional will fully explain the aspects of patient privacy concerning research specific information. In addition to signing the IRB Informed Consent, all patients must agree to the Research Authorization component of the informed consent form.

The participant must receive a copy of the signed informed consent form.

Remote Consenting

Patient will be consented remotely as part of this study either by phone.

During this phone call, or subsequent phone calls if necessary, the PI/treating physician will perform remote consent. The remote consent discussion will be documented in the medical record. Upon receipt/confirmation of the signed/dated consent form (if applicable), the authorized consenter will subsequently sign/date the scanned copy of the consent/HIPAA document, and provide documentation regarding the delay in signature, so documentation is clear and self-evident upon any audit or QA review. Further guidance regarding the consent process can be found in Appendix E: Consent Guidance.

7. TREATMENT PLAN

7.1 Agent Administration

Treatment will be administered on an inpatient basis. Reported adverse events and potential risks for BMS-986253 are described in **Section 10**. Appropriate dose modifications for BMS-986253 are described in **section 9**. No investigational therapies other than those described below may be administered with the intent to treat the patient's COVID-19 while the patient is enrolled in the study.

REGIMENT DESCRIPTION					
Agent	Premedications; Precautions	Dose	Route	Schedule ⁺	Cycle Length
BMS-986253	No specific premedications or precautions	2400mg	IV over 120 minutes (+/- 10 minutes)*	Days 1, 15, 29	6 weeks

*Infusion time will be 180 minutes (+/- 10 minutes) for patients <35kg.

⁺ Day 15 dose will be given if still hospitalized; day 29 dose is optional and will be given if patient hospitalized with severe respiratory symptoms.

7.2 Management of Infusion Reactions:

Since BMS-986253 contains only human Ig protein sequences, it is unlikely to induce hypersensitivity reactions. In the CA027-001 study, an infusion reaction (Grade 1) was observed in 1 patient and in the CA027-002 study 2 patients experienced infusions reactions (1 patient with Grade 2; 1 patient with Grade 4). If such a reaction were to occur, it might manifest with fever, chills, rigors, headache, rash, pruritus, arthralgia, hypotension, hypertension, bronchospasm, or other allergic-like reactions. All serious infusion reactions should be reported to BMS. All Grade 3 or 4 infusion reactions should be reported within 24 hours (excluding holidays and weekends) to the CUMC Sponsor-Investigator and BMS Medical Monitor and reported as an SAE. Infusion reactions should be graded according to NCI CTCAE v5.0 guidelines.

Treatment recommendations for infusion reactions are provided below and may be modified based on local treatment standards and guidelines, as appropriate.

For Grade 1 symptoms (mild reaction; infusion interruption not indicated; intervention not indicated):

- Remain at bedside and monitor participant until recovery from symptoms. The following prophylactic pre-medications are recommended for future infusions: diphenhydramine 50 mg (or equivalent) and/or acetaminophen/paracetamol 325 mg to 1000 mg at least 30 minutes before study treatment administrations.

For Grade 2 symptoms (moderate reaction requiring therapy or infusion interruption but responding promptly to symptomatic treatment such as antihistamines, non-steroidal anti-inflammatory drugs, narcotics, corticosteroids, bronchodilators, IV fluids, or prophylactic medications indicated for ≤ 24 hours):

- Stop the study treatment infusion, begin an IV infusion of 0.9% sodium chloride and treat the participant with diphenhydramine 50 mg IV (or equivalent) and/or acetaminophen/paracetamol 325 mg to 1000 mg; remain at bedside and monitor participant until resolution of symptoms. Corticosteroid and/or bronchodilator therapy may also be administered as appropriate. If the infusion is interrupted, then restart the infusion at 50% of the original infusion rate when symptoms resolve; if no further complications ensue after 30 minutes, the rate may be increased to 100% of the original infusion rate. Monitor participant closely. If symptoms recur, then no further BMS-986253 will be administered at that visit.
- For future infusions, the following prophylactic pre-medications are recommended: diphenhydramine 50 mg (or equivalent) and/or acetaminophen/paracetamol 325 mg to 1000 mg should be administered at least 30 minutes before study treatment infusions. If necessary, corticosteroids (up to 25 mg of hydrocortisone or equivalent) may be used.

For Grade 3 or 4 symptoms (severe reaction, Grade 3: prolonged [i.e., not rapidly responsive to symptomatic medication and/or brief interruption of infusion]; recurrence of symptoms following initial improvement; hospitalization indicated for other clinical sequelae [e.g., renal impairment, pulmonary infiltrates]; Grade 4: Life-threatening; pressor or ventilatory support indicated):

- Immediately discontinue infusion of study treatment. Begin an IV infusion of 0.9% sodium chloride and treat the participant as follows: recommend bronchodilators, epinephrine 0.2 mg to 1 mg of a 1: 1,000 solution for subcutaneous administration or 0.1 mg to 0.25 mg of a 1:10,000 solution injected slowly for IV administration, and/or diphenhydramine 50 mg IV with methylprednisolone 100 mg IV (or equivalent), as needed. Participant should be monitored until the investigator is comfortable that the symptoms will not recur. Study treatment will be permanently discontinued except for a Grade 3 infusion reaction that returns to Grade 1 in less than 6 hours. Investigators should follow their institutional guidelines for the treatment of anaphylaxis. Remain at bedside and monitor participant until recovery of the symptoms.

In case of late-occurring hypersensitivity symptoms (eg, appearance of a localized or generalized pruritus within 1 week after treatment), symptomatic treatment may be given (eg, oral antihistamine or corticosteroids).

7.3 General Concomitant Medication and Supportive Care Guidelines

7.3.1 Concomitant Therapy

The following medications are prohibited during the study if the subject is randomized to the investigational therapy arm (unless utilized to treat a drug related AE):

- anti-IL-6, anti-IL-6R antagonists or Janus kinase inhibitor (JAKi)

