In the ongoing Phase 1/2a Study CA027-002, the combination of BMS-986253 and nivolumab is being evaluated in advanced cancers. An ELISA assay is being used to detect serum free IL-8 (IL-8 that is not bound to therapeutic antibody). The serum free IL-8 results (as of the data cut-off date 16-Jan-2020) for 17 participants who were treated with BMS-986253 at a dose of 2400mg Q2W in combination with nivolumab 480 mg Q4W are presented in Figure 3. All participants displayed a rapid decrease in free serum IL-8 at the earliest time point assessed (Cycle 1 Day 2). **The data suggest that BMS-986253**

Figure3 Free serum IL-8 concentration after treatment with BMS-986253

decreases free serum IL-8 in a dose and frequency dependent manner. The 2,400 mg Q2W dosing provides the deepest and most durable free serum IL-8 suppression as well as robust suppression of IL-8 in tumor tissue.

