g: If randomized to anti-IL-8 therapy, BMS-986253 will be given every 2 weeks (+/- 2 days). 2nd dose will be given if patient is still hospitalized. 3rd dose is optional and will be given if patient still hospitalized with severe COVID-19. If randomized to control, patients will receive standard of care as determined by their treating physician.
h: Follow-up for toxicity will be done until 100 days following last dose of treatment
i: Vitals signs should include temperature, heart rate, blood pressure, respiratory rate and oxygen saturation and FIO₂ if on supplemental oxygen
j: Inflammatory markers will include: LDH, D-Dimer, CRP, sIL-6 (+/- 1 day).
k: Documented physical exam from primary treatment team will be sufficient with chart review by research team.
l: 7-point ordinal scale scored as follows: (1) death, (2) hospitalized on invasive mechanical ventilation or extracorporeal membrane oxygenation, (3) hospitalized, requiring non-invasive ventilation or high flow nasal cannula, (4) hospitalized, requiring supplemental oxygenation (5) hospitalized, not requiring supplemental oxygenation and requiring ongoing medical care (COVID-19 related or otherwise) (6) Hospitalized, not requiring supplemental oxygen – no longer requires ongoing medical care, (7) not hospitalized.

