Change in sIL-6 levels before and after treatment and over time will be measured every other day during hospitalization.

11.2.10 *Radiographic response*

Radiological response will be evaluated by comparing % of lung fields with infiltrates on chest imaging (CXR and CT) through independent radiology review between baseline and day 8) if available.

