13.2 Study Endpoints and Analysis Plan

All subjects who receive at least one dose of study drug will be considered evaluable and included in the efficacy and safety analysis.

Analytic plan for primary objective:

The primary efficacy null hypothesis of the equality of time to improvement (2 points) in clinical status curves will be tested with the log-rank test. The overall type I error for the primary analysis will be considered one-sided alpha of 0.025. Kaplan-Meier estimates will be reported for each of the two arms with median time to improvement and 95% confidence intervals (CI). Cox regression will be employed to estimate the treatment effect (HR) and 95% CI.

Analytic plan for secondary and exploratory objective:

We will estimate the distributions of all time-to-event endpoints using the Kaplan-Meier method and if possible, provide medians (95% CI). Comparisons between survival curves will be assessed using log-rank tests and Cox regression models.

For each arm, we will estimate the 1-month mortality rate and incidence of adverse events graded by CTCAE v5.0 using the exact 95% confidence intervals. Comparisons between the two arms will be assessed using chi-squared or Fisher's exact tests. The mean/medians of the 7-point ordinal scores at day 14 after the start of treatment will be computed and compared between the two groups using two-sample t-test or the equivalent non-parametric Wilcoxon Rank-Sum test if normality is not satisfied.

Changes in exploratory endpoints (before and after treatment) will be quantified using means (95% CI) and/or medians (inter-quartile ranges) for non-normal data. Comparisons between the two arms will be made using two-sample independent t-tests or the non-parametric equivalent, Wilcoxon Rank-Sum test. The associations between baseline levels and/or changes over time of IL-8 and other key cytokines (TNF, IL-1b, IL-6) with outcomes will be assessed using regression models.

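### A between-arm difference in IL-6 cannot be credited to anti-IL-8 if controls receive the anti-IL-6, anti-IL-6R or JAK agents that Section 7.3.1 bars only in the anti-IL-8 arm

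*Combined protocol and SAP*

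**What the plan says.** Section 7.3.1 states that anti-IL-6 drugs, anti-IL-6R antagonists and JAK inhibitors are "prohibited during the study if the subject is randomized to the investigational therapy arm (unless utilized to treat a drug related AE". It sets no matching bar for controls. Footnote g of the study calendar (Section 10) says: "If randomized to control, patients will receive standard of care as determined by their treating physician". Section 5.2 excludes patients at entry for "Treatment with anti-IL-6, anti-IL-6R antagonists or Janus kinase inhibitor (JAKi) within 48 hours of first dose of study treatment", but does not govern later use.

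The change in sIL-6 is an exploratory endpoint. Section 11.2.9 says: "Change in sIL-6 levels before and after treatment and over time will be measured every other day during hospitalization". Section 11.2.15 adds circulating IL-6 at baseline and, where possible, on days 8, 15, 22 and 29.

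For changes in exploratory endpoints as a class, Section 13.2 says: "Comparisons between the two arms will be made using two-sample independent t-tests or the non-parametric equivalent, Wilcoxon Rank-Sum test". It also plans to relate cytokines to outcome. Associations of baseline levels and/or "changes over time of IL-8 and other key cytokines (TNF, IL-1b, IL-6) with outcomes will be assessed using regression models".

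**The concern.** Two of the three restricted drug classes act directly on the IL-6 pathway that is being measured, and only controls may receive them freely. A control sample drawn after such a drug carries the drug's own effect on measured IL-6, while almost no anti-IL-8 sample does. The planned test pools all samples, so its result mixes any effect of anti-IL-8 with the effect of the controls' drug.

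At stake is the mechanistic reading. A difference could appear when anti-IL-8 does nothing to IL-6, or a real effect could be hidden. The same samples enter the regression of outcome on change in IL-6.

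**Working it through.** **Does another provision close the gap?** The plan states no figure on this point, so the first check is textual.

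- Section 5.2 bars investigational COVID-19 therapy given within another trial, but excepts "other treatments being used as compassionate use or under Emergency Use Authorization (EUA) for COVID-19 per Investigator discretion".
- Section 7.1 bars other investigational therapies. It does not reach a drug that the physician uses as standard care.
- The per-protocol set (13.5.1) serves only the primary endpoint, and control use would not breach 7.3.1.
- Section 13.2 does not exclude, flag or adjust for such samples.

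Nothing closes the gap.

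**Inputs.** From the documents: 92 and 46 patients (13.1) and sampling every other day (11.2.9). Assumed, because the documents give none of it:

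- two-sided 5% test on the change to day 7;
- SD of ln sIL-6 of 1.2, within-patient correlation 0.6, and a decline of 0.15 ln units per sample;
- control use q of 10, 20 or 40%, more likely at high sIL-6;
- measured sIL-6 shifted 3-fold in either direction, or 10-fold upward, after the agent.

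**Bias.** If a share q of controls has its ln change shifted by δ, and anti-IL-8 has no effect, the expected anti-IL-8 to control ratio is about exp(-qδ).

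- q = 0.40, 3-fold fall: exp(0.40 × 1.099) = 1.55.
- q = 0.40, 10-fold rise: exp(-0.40 × 2.303) = 0.40.

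Simulation gave 1.56 down to 0.39, against a true 1.00.

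**Bias against the significance threshold.**

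- SD of change = 1.2 × √(2 × (1 - 0.6)) = 1.073.
- SE = 1.073 × √(1/92 + 1/46) = 0.194, and 1.96 × SE = 0.380.
- The bias alone reaches this at q = 0.380/ln 3 = 35%, or 0.380/ln 10 = 16%.

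**Simulated rejection, all samples, t-test, no anti-IL-8 effect.**

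| Control use | 3-fold shift | 10-fold rise |
|---|---|---|
| 10% | 7-11% | 22% |
| 20% | 18-20% | 56% |
| 40% | 57-60% | 97% |

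A rerun gave about 10%, 20% and 56-60% for the 3-fold shift, and 21%, 56% and 98% for the 10-fold rise. Across the same settings the Wilcoxon test rejects in 5-60% (3-fold) and 21-98% (10-fold). An agent with no effect on the assay leaves the t-test at about 5% (5.3% in 20,000 runs).

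A simpler simulation in SD units shows the same pattern. A shift of 1 SD is close to 3-fold (ln 3/1.073 = 1.02), and gave 8% at 10% use and 27% at 25% use. A shift of 2 SD is near 10-fold (ln 10/1.073 = 2.15), and gave 19% and 68%.

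**Mixed model on samples before the agent, same assumptions.**

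- No anti-IL-8 effect: ratio 0.98-1.00, rejection 3.6-5.8%.
- True ratio 0.60, 3-fold shift, 20-40% use: the model gives 0.59-0.60 with power 69-79% (84% with no use). The all-samples t-test gives 0.39-0.94 with power 9-99.7% (74% with no use).
- About half discharged by day 7: model 5.6-6.9%, all samples 7-96%.
- Agent started for reasons not visible in earlier sIL-6: model ratio 1.07-1.15 and rejection 6-10%; all samples 0.40-1.53 and 23-97%.

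These runs used 700 to 1,000 replicates (Monte Carlo SE about 0.7-0.9 points near 5%), so small differences between model figures mean little.

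**The case against.** The strongest reply is about the question being asked. The trial compares anti-IL-8 with physician-chosen care, and how sIL-6 moves under each assigned strategy is a valid question. The sIL-6 objective in Section 2.1 does not ask for a comparison with an untreated control state. **This stands.** A reader might infer from the table that the planned test is invalid or has a false-positive rate of up to 97%. The documents do not support that. Those rejections are errors only if the result is read as anti-IL-8's own effect on IL-6.

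The premise is also inferred. No sentence says that controls will receive these agents; it follows from the one-sided wording of 7.3.1 and physician choice. How often it would happen is unknown. **This stands**, and it makes the size conditional without removing the gap.

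The effect on the assay is not documented either. Section 3.4.3 reports that "All participants displayed a rapid decrease in free serum IL-8 at the earliest time point assessed" after BMS-986253. That shows that an antibody can change the measured level of its own target. It does not show what an anti-IL-6, anti-IL-6R or JAK agent does to the sIL-6 assay in this trial, in size or direction.

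Finally, restricting to pre-agent samples is a different estimand with its own bias, since it drops post-randomization samples mainly in controls. **This stands**, and is why it should supplement the planned comparison and not replace it. A table of use alone would show exposure, but would not show whether the IL-6 result depends on it.

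**Conclusion.** The point holds in a limited form. As planned, the comparison of sIL-6 and circulating IL-6 is a contrast of treatment strategies. It does not isolate the effect of anti-IL-8 if controls receive the restricted agents. The distortion is nil with no control use. Under the assumptions above it is modest at 10% use with a 3-fold shift (7-11% rejection) and dominant at 40% use (57-60%, or 97% for a 10-fold rise). Every use rate, effect size and variance is assumed.

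Two wider readings are not supported. A reader might infer that the clinical endpoints are compromised; for those, comparison with physician-chosen care is what the trial sets out to make, so the primary and clinical secondary results are untouched. A reader might also infer that use before the 48-hour window in 5.2 biases the arms; such use precedes randomization and is balanced in expectation.

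This is a minor point about exploratory biomarker conclusions.

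**What to change.** In Section 13.2:

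1. Keep the all-samples comparison of sIL-6 and circulating IL-6, labelled as a treatment-strategy contrast.
2. Add a supplementary repeated-measures mixed model on log values, using only samples up to the first anti-IL-6, anti-IL-6R or JAK inhibitor dose in either arm, including a dose given for a drug-related adverse event.
3. Tabulate use of these agents and day of first dose by arm.
4. Repeat the IL-6 regression with the same pre-agent values as a sensitivity analysis.
5. State in advance that an IL-6 difference will be attributed to anti-IL-8 only if the two analyses agree.

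The cost is a few sentences and one table. No new data are needed: Section 10.2 already has medications reviewed daily and sIL-6 drawn every other day. The downside is lost precision, because later samples are set aside mainly in controls (power 69-79% at 20-40% use in the setting above, against 84% with none). The model is also biased if starting an agent depends on factors not recorded in earlier values.
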